## 3 Study Design

### 3.1 General Design

In this pilot randomized double blind placebo controlled study we wish to assess the ability of oral  $\omega$ 3 free fatty acids to downregulate pro-neoplastic and pro-inflammatory pathways in the esophagus. Pilot data from this proposal will enable us to design a larger adequately powered study assessing the role of  $\omega$ 3 free fatty acids as chemoprevention agents in subjects with BE, who are at substantial risk of developing EAC, a lethal cancer with rapidly rising incidence in the United States. Our plan is to complete the study on 80 participants, 40 in each group randomized to omega-3 or placebo. Subjects between 18-85 years of age, with known BE (no dysplasia and low-grade dysplasia) will be identified using an existing GI database for participation in this study. Invitation letters will be mailed to eligible subjects. Subjects meeting inclusion and exclusion criteria will be screened and consented. Once consent has been obtained baseline assessment and endoscopy with biopsy/brushings, and endoscopic mucosal impedance measurement will be completed. A single slice CT scan of the abdomen will also be obtained at baseline for each subject to quantify visceral and subcutaneous fat area in the abdomen. Subjects will then begin treatment and follow-up for the next 6 months. A final visit for evaluation and collection of tissue samples will be conducted at the end of the study. No risks of any particular seriousness or severity are anticipated. Blood and tissue samples will be obtained and used in this study as outlined in section 3.2. Any remaining samples will be stored in [name] -80C freezer located at Joseph M97 and used for future research in Barrett's esophagus.

Modulation of Esophageal Inflammation in Barrett's Esophagus by  $\omega$ 3 Fatty Acids

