### **5.3 Method for Assigning Subjects to Treatment Groups**

A randomization schedule will be generated in the Division of Biomedical Statistics and Informatics and sent to the research pharmacy. Investigators and patients will be blinded to drug versus placebo assignment and only research pharmacy personnel and statisticians will have access to the assignments until the study is completed. Medications (drug and matching placebo) will be dispensed through the Mayo research pharmacy.

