## 7 Statistical Plan

### 7.1 Sample Size Determination

#### Statistical Analysis

Up to 90 patients with Barrett's will be identified and randomized to either drug or placebo. The primary analysis objective in this pilot study is to estimate response magnitude and variation which will be the information needed to design a larger adequately powered study to study the efficacy of  $\omega$ 3FFA as a chemoprevention agent in BE. The data will be summarized as mean, standard deviation, as well as median, and interquartile range, overall (baseline) and by treatment group (post-supplementation at 6 months). In addition, 95% confidence intervals for response mean (or median) treatment group values and 95% confidence intervals for treatment group differences in means (or medians) will also be calculated. Exploratory descriptive summaries of the response data will also be generated after stratifying on ASA intake.

Aim 1: The primary response outcome is tissue PGE2 levels and the main secondary response outcome is the histologic score of 3 or 4 (severe grades of inflammation). Other secondary outcomes include pre and post supplementation serum and tissue  $\omega$ 3 FFA levels.

Aim 2: The primary response outcome is the Cytokine expression profile in esophageal biopsies as measured by qPCR [IL1 $\beta$ , IL6 (M1 markers) versus IL1, IL10 (M2 markers)]. Secondary response outcomes include change in esophageal macrophage counts and phenotype proportions (total, %M1, %M2).

Aim 3: The esophageal mucosal impedance of the squamous epithelium and columnar epithelium will be summarized as mean (SD) or median (IQR) depending on data normality. The data will be summarized (baseline and post-supplementation) by treatment group. Change in impedance (Baseline – post supplementation) will be compared using appropriate statistical tests. Secondary outcome analysis will include testing the association between esophageal mucosal impedance and measures of central obesity (including waist circumference, waist hip ratio and abdominal visceral fat area on CT scan).

Aim 4:

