**Pitfalls and Alternative approaches:** It is possible that recruitment to this trial may be challenging. However, more than 400 patients with BE are seen annually in Rochester and the PI has successfully led and participated in many prospective studies which have recruited BE patients for clinical trials. It also possible, though unlikely, that the in-vitro effects of  $\omega$ 3 FFAs may not translate into clinical effects in terms of alterations in tissue PGE2 and macrophage counts. We will also consider assessing the influence of  $\omega$ 3 FFA on BE cell survival, a known biological correlate to neoplastic progression in BE, using Ki-67-Caspase dual staining to assess other biologic effects of  $\omega$ 3 FFA. Concomitant ASA use may confound the effects on PGE2 levels. Given that this is a preliminary study, we will collect data on ASA and NSAID use and perform analysis stratified on ASA and NSAID use. The randomized study design will however mitigate this confounding effect to a large extent. It is possible that the dose of  $\omega$ 3 FFA used in this proposal may be inadequate for a clinical effect in vivo. We have chosen the 3.6 grams/day dose as described in prior human clinical trials: this dose has been shown to be well tolerated and able to produce meaningful clinical response in human trials. We also have proposed to target subjects with a BMI>30 given that these subjects with increased visceral fat are most likely to benefit from  $\omega$ 3 FFAs.

**Feasibility and Timeline:** We anticipate recruitment to be complete in 6-9 months following IRB approval (which has been initiated). Assays and analysis should be completed in 3 months following completion of the trial and publication thereafter. Assays have been previously performed and validated in multiple published manuscripts by collaborators and Core laboratories. Preliminary data obtained from this trial will be crucial in supporting an aim of a R01 application focused on assessing the mechanistic relationship between BE and central obesity.

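### The month-6 PGE2 comparison has no prespecified estimate adjusted for baseline PGE2 and ASA/NSAID use, although the plan says ASA may confound PGE2

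*Combined protocol and SAP*

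**What the plan says.** Section 7.1, Statistical Analysis, states for Aim 1: "The primary response outcome is tissue PGE2 levels". The between-arm analysis is given as "95% confidence intervals for treatment group differences in means (or medians) will also be calculated". No covariate is attached to it, and baseline PGE2 is to be summarised overall rather than used in the comparison.

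ASA is handled in two places in section 7.1:

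- Statistical Analysis: "Exploratory descriptive summaries of the response data will also be generated after stratifying on ASA intake".
- Pitfalls and Alternative approaches: after naming ASA as a possible confounder of PGE2, the plan will collect ASA and NSAID data and "perform analysis stratified on ASA and NSAID use". It then adds "The randomized study design will however mitigate this confounding effect to a large extent".

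On allocation, section 5.3 says only "A randomization schedule will be generated in the Division of Biomedical Statistics and Informatics and sent to the research pharmacy". Sections 4.3 and 5.6 add no stratification factor, block size or minimisation rule. Section 4.2 does not exclude ASA or NSAID users. Section 5.5 has all medications, including over-the-counter ones, listed at baseline, and section 3.2 has PGE2 measured at baseline and at 6 months.

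On size, section 3.1 says "Our plan is to complete the study on 80 participants, 40 in each group randomized to omega-3 or placebo" and section 7.1 says "Up to 90 patients with Barrett's will be identified and randomized to either drug or placebo".

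**The concern.** The plan names a covariate that may affect its primary outcome, records it before treatment starts, and leaves it out of the main estimate. The two statements on ASA do not match. One covers ASA only and is descriptive and exploratory. The other covers ASA and NSAIDs and is called an analysis, without a method. Neither says how the strata would be combined into one treatment effect, so two analysts could report different results and both claim to have followed the plan.

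The pilot exists to supply a response magnitude and a variation for a larger trial, and the omission touches both. A chance difference in ASA use between arms moves the estimated magnitude. ASA variation left in the SD enlarges the variation carried into the next sample size.

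**Working it through.** **Figure to reproduce.** There is none. Section 7.1 gives no SD, target precision or power for PGE2, and the readable text of the preliminary data in section 1.1 gives group means without an SD.

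**Inputs.**
- n = 40 per arm (section 3.1); 45 per arm as a check (half of the 90 in section 7.1).
- p, proportion using ASA: 0.2 to 0.5. Assumption.
- g, effect of ASA on month-6 PGE2, in SDs within ASA stratum: 0.5 to 1.0. Assumption.
- Simple 1:1 randomisation. Assumption, since the documents do not say how the schedule is built.

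**Step 1: imbalance in ASA use.** SD of the between-arm difference = sqrt(2p(1-p)/n). For p = 0.2 this is sqrt(2 × 0.16/40) = 0.089. The probabilities are exact, from two independent binomials at n = 40.

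| p | SD of imbalance | P(10 points or more) | P(20 points or more) |
|---|---|---|---|
| 0.2 | 0.089 | 0.326 | 0.035 |
| 0.3 | 0.102 | 0.393 | 0.067 |
| 0.4 | 0.110 | 0.424 | 0.086 |
| 0.5 | 0.112 | 0.434 | 0.093 |

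At 45 per arm, P(10 points or more) is 0.234 to 0.343.

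**Step 2: shift in the PGE2 difference.** Shift = g × imbalance. At 10 points it is 0.05 SD (g = 0.5) or 0.10 SD (g = 1).

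**Step 3: precision.** The total variance is 1 + g²p(1-p) in within-stratum units. Unadjusted half-width = 1.96 × sqrt(2(1 + g²p(1-p))/40). Adjusted half-width = 1.96 × sqrt(2/40) = 0.438 SD.

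| p | Unadjusted, g = 0.5 | Unadjusted, g = 1 |
|---|---|---|
| 0.2 | 0.447 | 0.472 |
| 0.3 | 0.450 | 0.482 |
| 0.4 | 0.451 | 0.488 |
| 0.5 | 0.452 | 0.490 |

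Narrowing = 1 - 1/sqrt(1 + g²p(1-p)). For g = 0.5 it runs from 1 - 1/sqrt(1.04) = 2% to 1 - 1/sqrt(1.0625) = 3%. For g = 1 it runs from 1 - 1/sqrt(1.16) = 7% to 1 - 1/sqrt(1.25) = 11%. The adjusted formula ignores the small cost of estimating the ASA effect. In simulation the stratified estimate had an SD of 0.224 to 0.226, against 0.2236 by formula.

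**Step 4: carry-over to the next trial.** From the same factors, the unadjusted PGE2 variance is 4-6% larger (g = 0.5) or 16-25% larger (g = 1) than the within-stratum variance. A later trial that adjusts for ASA but takes its SD from the unadjusted summary would overstate its sample size by about that much.

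**Step 5: bias and coverage.** Simulation used 100,000 trials per scenario, with p = 0.3 and 0.4, g = 0.5 and 1, and 40 per arm. Mean bias of the unadjusted difference was about 0 and overall 95% coverage was 0.949 to 0.951. Among trials with imbalance of 20 points or more, coverage was about 0.93 (g = 0.5) or 0.87-0.88 (g = 1).

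**The case against.** The case for leaving the plan alone has real weight.

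- **Randomisation does its job.** The unadjusted difference is unbiased and its interval has nominal coverage, so the plan's statement about randomisation is defensible. A reader might infer a biased primary estimate; step 5 shows otherwise. What remains is precision, and error conditional on an imbalance in the one trial run.
- **ASA is not ignored.** A reader might infer that randomisation is the only safeguard. The documents do not support that, because a stratified analysis is promised immediately before the randomisation sentence. The gap is its specification.
- **Unstratified allocation is not stated.** Sections 4.3, 5.3 and 5.6 are silent on the method. A reader might infer simple randomisation, but the schedule may already be stratified, which would reduce the probabilities in step 1.
- **NSAIDs are not called a confounder.** Only ASA is. NSAIDs enter through the stratified analysis.
- **Large imbalances are a tail case.** At p = 0.4 the edge of the 95% range is 1.96 × 0.1095 = 21.5 points, which would shift the estimate by 0.107-0.215 SD. The median imbalance is about 0.674 × 0.1095 = 7.4 points, a shift of 0.04-0.07 SD, or about 8% (0.037/0.451) to 15% (0.074/0.488) of the half-width.
- **Baseline PGE2 may absorb part of the effect.** Aim 1 in section 2 speaks of changes, and a stable ASA effect present at both visits would largely cancel in a change score. Section 7.1, however, specifies PGE2 levels and makes no use of baseline in the arm comparison. This lowers the likely size of the shift and strengthens the case for a baseline term.
- **This is an estimation pilot.** No powered test depends on the choice.

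These points limit the size of the problem. They do not supply the missing adjusted estimate or reconcile the two statements on ASA.

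**Conclusion.** The point holds as a low-cost improvement, not as a flaw that invalidates the primary estimate. The plan identifies a possible confounder of PGE2, collects it together with baseline PGE2, and prespecifies an arm comparison that uses neither. Its two ASA analyses differ in scope and status, and neither yields a pooled adjusted effect.

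The size is modest unless ASA has a large effect. An imbalance of 10 points or more is fairly likely (0.33-0.43), but at 10 points the shift is 0.05-0.10 SD against a half-width of 0.45-0.49 SD. The precision gain from ASA alone reaches 7-11% only if the ASA effect is 1 SD. All of this rests on assumed prevalence, assumed effect, simple randomisation and the full ASA effect acting on month-6 levels. The finding that no adjusted estimate is specified, and that the two statements differ, needs none of these assumptions.

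**What to change.** 1. Define one binary baseline factor, ASA or NSAID use (yes/no), stating what counts as use. Apply the same definition in both parts of section 7.1.
2. Prespecify the month-6 PGE2 arm difference with its 95% CI from a model adjusted for baseline PGE2 and that factor. Fix the analysis scale in advance, since the plan leaves means or medians open.
3. Report the residual SD from that model beside the unadjusted SD, so that the later trial can use the one that matches its own analysis.
4. State in section 5.3 whether the schedule is stratified. Stratifying it by the same factor is optional, and applies only if it is not already stratified or in use.

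The cost of items 1 to 3 is one model on data already planned, and they remain available after randomisation has begun; they are best fixed before unblinding. Item 4, if taken up, needs separate lists for users and non-users, and the pharmacy must know ASA/NSAID status before each assignment.

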## 8 Safety and Adverse Events

### Adverse event grading

Attribution scale. An adverse event is defined as both an expected side effect that is of a serious nature, or an unexpected side effect/event regardless of severity. All events will be graded as to their attribution (unrelated to protocol, or possibly, probably, or definitely related to protocol).

Any event that is reported to either the principal investigator or his designated research associates by the subject or medical staff caring for the subject and which meets the criteria will be documented as such.

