### **3.3 Primary Safety Endpoints**

$\omega$ 3 FFAs have an excellent safety and tolerability profile. Most common side effects associated with their use in human trials include diarrhea, indigestion, nausea, fishy taste and belching. Total incidence of GI disturbances in phase 2 and 3 clinical trials has varied between 1.4 – 4.9%, with a very low rate of study termination [27]. The rate of study withdrawal was 3.4% in a phase 3 study using EPA [20].

We will specifically assess the prevalence of adverse effects in subjects randomized to drug or placebo. Adverse effects which have been reported in the literature, may include:

1. Gastrointestinal adverse effects such as: abdominal pain, nausea, vomiting, diarrhea.
2. Altered (fishy) taste in the mouth. The preparation used in this trial using orange oil to mask this effect.
3. Allergic reactions.
4.  $\omega$ 3 FFAs have antiplatelet activity, however increased rates of bleeding have not been seen in large clinical cardiovascular trials [28]. We will specifically assess rates of any mucosal or skin bleeds in monthly telephone calls (1,2,3,4,5 months) and at the 6 month visit.

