### **8.1 Definitions**

#### **Unanticipated Problems Involving Risk to Subjects or Others (UPIRTSO)**

Any unanticipated problem or adverse event that meets the following three criteria:

- **Serious:** Serious problems or events that results in significant harm, (which may be physical, psychological, financial, social, economic, or legal) or increased risk for the subject or others (including individuals who are not research subjects). These include: (1) death; (2) life threatening adverse experience; (3) hospitalization - inpatient, new, or prolonged; (4) disability/incapacity - persistent or significant; (5) birth defect/anomaly; (6) breach of confidentiality and (7) other problems, events, or new information (i.e. publications, DSMB reports, interim findings, product labeling change) that in the opinion of the local investigator may adversely affect the rights, safety, or welfare of the subjects or others, or substantially compromise the research data, **AND**
- **Unanticipated:** (i.e. unexpected) problems or events are those that are not already described as potential risks in the protocol, consent document, not listed in the Investigator's Brochure, or not part of an underlying disease. A problem or event is "unanticipated" when it was unforeseeable at the time of its occurrence. A problem or event is "unanticipated" when it occurs at an increased frequency or at an increased severity than expected, **AND**
- **Related:** A problem or event is "related" if it is possibly related to the research procedures.

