#### **Adverse Event**

An untoward or undesirable experience associated with the use of a medical product (i.e. drug, device, biologic) in a patient or research subject.

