#### **Serious Adverse Event**

Adverse events are classified as serious or non-serious. Serious problems/events can be well defined and include;

- death
- life threatening adverse experience
- hospitalization
- inpatient, new, or prolonged; disability/incapacity
- persistent or significant birth defect/anomaly

and/or per protocol may be problems/events that in the opinion of the sponsor-investigator may have adversely affected the rights, safety, or welfare of the subjects or others, or substantially compromised the research data.

In case of a serious adverse event, the PI or a member of the study team will contact the research pharmacy for unblinding of the randomization code.

All adverse events that do not meet any of the criteria for serious, should be regarded as **non-serious adverse events**.

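### Section 8's opening definition of an adverse event contradicts sections 3.3, 8.1 and 8.2, so it is unclear whether expected non-serious effects reach the adverse event record and the comparison by arm

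*Combined protocol and SAP*

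**What the plan says.** Section 8 contains two definitions of an adverse event.

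- **Section 8, Adverse event grading.** The definition begins "An adverse event is defined as both an expected side effect that is of a serious nature". In full, two kinds of event qualify: "an expected side effect that is of a serious nature, or an unexpected side effect/event regardless of severity". The next paragraph says that an event reported to the investigator or the research staff "which meets the criteria will be documented as such".
- **Section 8.1, Adverse Event.** The definition is "An untoward or undesirable experience associated with the use of a medical product". It does not mention expectedness or seriousness. The Serious Adverse Event entry that follows adds: "All adverse events that do not meet any of the criteria for serious, should be regarded as" non-serious adverse events, so non-serious events remain adverse events.

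Section 8.2 requires all adverse events to be entered in the source document and in the adverse event part of the case report form. Section 8.3 starts the worksheet and log once an adverse event has been identified.

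Section 3.3 (Primary Safety Endpoints) states: "We will specifically assess the prevalence of adverse effects in subjects randomized to drug or placebo". Its list opens with "Gastrointestinal adverse effects such as: abdominal pain, nausea, vomiting, diarrhea" and goes on to altered taste, allergic reactions, and bleeding from mucosa or skin. Sections 4.3 and 5.4 have the coordinator ask each month about adverse effects, both presence and grade. Section 5.4 ties those questions to the section 3.3 list.

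**The concern.** The effects in section 3.3 are mostly ones already known for omega-3 preparations, and many will be mild. These are the events that the opening definition of section 8 leaves out. Taken by itself, that definition would keep most of what the safety endpoint is meant to count off the adverse event record.

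Because section 8.1 says something different and neither definition is declared to prevail, two coordinators could handle the same report of mild nausea differently, each with support in the protocol. The by-arm prevalence promised in section 3.3 would then partly reflect which definition was used. The effects at risk are also those for which a difference between drug and placebo is most plausible.

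**Working it through.** There is no plan figure to reproduce. The check sets the rules side by side and then gives a rough scale.

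**Step 1: which effects are expected?** The opening of section 8 does not define the word. The nearest guide is the UPIRTSO entry in section 8.1, which equates unanticipated with unexpected and applies it to events "not already described as potential risks in the protocol" (or in the other listed sources). The effects in section 3.3 are described there as reported or possible. By that guide, gastrointestinal symptoms and fishy taste are expected. Bleeding is less clear: section 3.3 notes antiplatelet activity but says that raised bleeding rates were not seen in large trials.

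**Step 2: apply each rule.**

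| Type of event | Section 8 opening | Section 8.1 | Section 3.3 endpoint (listed effects) |
|---|---|---|---|
| Expected, serious | counts | counts | counts |
| Unexpected, any severity | counts | counts | counts if listed |
| Expected, non-serious | does not count | counts | counts |

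The rules differ only in the last row, which holds non-serious gastrointestinal symptoms, fishy taste and, arguably, minor bleeds.

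**Step 3: does another rule settle it?**

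- Sections 8.2 and 8.3 both act on adverse events, the term in dispute, so they inherit the ambiguity.
- Sections 3.3, 4.3 and 5.4 speak of adverse effects. They do not say that a solicited non-serious effect is entered in the adverse event part of the case report form.
- The statistical plan (section 7) gives no safety analysis, so it does not fix what is tabulated.

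**Step 4: scale, for illustration.** Inputs are 40 per arm (section 3.1) and a gastrointestinal incidence of 1.4% to 4.9% (section 3.3, cited from other trials). Applying that incidence to this population is an assumption.

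- Expected subjects per arm, n × p: 40 × 0.014 = 0.56 and 40 × 0.049 = 1.96.
- Probability of at least one in an arm, 1 − (1 − p)^n: 1 − 0.986^40 = 0.431 and 1 − 0.951^40 = 0.866.
- Section 7.1 allows up to 90 randomized. With an equal split, 45 per arm gives 45 × 0.014 = 0.63 and 45 × 0.049 = 2.21.

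If all of these were expected and non-serious, the section 8 opening alone would document 0 of them as adverse events, and section 8.1 would count every one.

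**The case against.** The best defence is that the safety endpoint does not run through the opening paragraph of section 8. Section 3.3 names the effects with no filter, section 5.4 has them asked about by name with presence and grade, and the Schedule of Events has adverse event evaluation at months 1 to 6 and again 7 days later. The definition under the heading Definitions is the broad one, and the section on recording says all adverse events. A sensible coordinator would probably record everything.

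Much of this stands, and it limits the point. A reader might infer that the plan removes the gastrointestinal, taste and bleeding effects from the safety endpoint. The documents do not support that: the effects are still solicited, their serious forms count under either definition, and a bleed might be judged unexpected and so count at any severity. The UPIRTSO entry also treats an event that is more frequent or more severe than expected as unanticipated.

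A reader might also infer that recorded counts will fall to near zero, or that a tolerability rate set too low will be passed to the larger trial. The first would require staff to apply the opening definition and ignore sections 3.3, 5.4, 8.1 and 8.2, and no figure in the documents gives the share of effects that are non-serious. On the second, sections 3.2 and 7.1 say that the pilot passes on the size and variation of response in inflammation and injury outcomes. They mention no tolerability rate.

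The defence does not remove the contradiction. Good practice by coordinators would mean setting aside a definition that the protocol states in plain terms.

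**Conclusion.** Wrong as written. The opening definition in section 8 cannot be held together with sections 3.3, 8.1 and 8.2. This is a false rule in the text, not a missing detail. The consequence is uncertainty about whether expected non-serious effects are recorded as adverse events and enter the comparison by arm. Loss of the endpoint is not shown.

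The affected number is small in absolute terms, about 0.6 to 2.0 subjects with gastrointestinal effects per arm of 40. That rests on the cited incidence applying here. The contrast of none against all also requires every such effect to be non-serious and judged expected. Counts this low would not support an informative comparison under either definition, but the choice of definition could decide whether any event appears at all. No efficacy outcome, sample size or randomization element is touched.

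**What to change.** Delete the definition in the opening of section 8 and use the section 8.1 definition throughout. Add one sentence, in section 8.2 or 3.3: every section 3.3 effect reported at a monthly call or at Visit 2 is recorded on the case report form with grade and attribution, whether or not it is expected or serious. Add to the statistical plan that these effects are tabulated by arm.

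The cost is wording and a few more log entries. The calls already ask for presence and grade, so no new data collection is needed.
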